We specified hypotheses based upon the pattern of results found through child age 12, and separated them into primary and secondary hypotheses. Following the original formulation of hypotheses, we edited them to take into account results from the earlier Elmira trial¹⁰ that were analyzed following the submission of the proposal for the current phase of follow-up in Memphis. We had originally hypothesized that program effects would be more pronounced for mothers and children living in the most disadvantaged neighborhoods in Memphis, but realized as these data were being gathered that virtually all of the participants in the Memphis trial lived in neighborhoods that were so disadvantaged that there was little meaningful variation among neighborhoods, and therefore removed this aspect of our hypotheses. We also found that it was impossible to consistently gather information from children's school records on outcomes like conduct grades from hundreds of schools, so substituted high school graduation as a secondary outcome. These refined hypotheses were specified prior to the completion of data gathering and any analysis of treatment-control differences. We specify the original hypotheses and then indicate the revised hypotheses for maternal and child outcomes. Compared to control-group counterparts:

Original Maternal Outcomes Hypotheses

1. **(Primary)** The program will continue to improve maternal life-course (fewer short inter-birth intervals, less use of welfare, more stable partner relations), especially for mothers with higher psychological resources.
2. **(Secondary)** The program will reduce maternal substance use disorders (SUDs) and depression, effects that will be more pronounced for a) mothers with low psychological resources, and b) those living in the most disadvantaged neighborhoods at registration.

Revised Maternal Outcome Hypotheses

1. **(Primary)** The program will continue to improve maternal life-course (reflected in total costs of welfare – SNAP, TANF, Medicaid), especially for mothers with higher psychological resources.
2. **(Secondary)** The program will reduce maternal substance use disorders (SUDs) and depression.

Original Child Outcomes Hypotheses

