Of particular note, there was a trend ($p=.08$) for nurse-visited firstborn children to die less frequently in the first 9 years of the child’s life (10/498 vs. 1/222 live births);⁷ 9 of the 10 control-group deaths were due to preventable causes (preterm delivery, Sudden Infant Death Syndrome, or injury); one death in the control group and the only death in the nurse-visited group were due to non-preventable causes (chromosomal anomalies, multiple congenital anomalies)⁷ Two of the injury deaths in the control group were by firearm. By age 12, another nurse-visited child had died due to a brain tumor (not preventable). When viewed in light of earlier program effects on childhood injuries, these mortality data suggest that nurses helped parents reduce their children’s exposure to serious, life-threatening adversities.

Table 1. Program effects on selected prenatal health, care-giving, injuries, maternal life-course, and child outcomes through child age 12

Variable	Sample	Comparison	Nurse	Comp vs. Nurse	
		Mean/Rate	Mean/Rate	p-value	Effect
Prenatal Health after Enrollment					
Pregnancy induced hypertension, %	Whole	20.0	13.0	.009	OR=0.65
Incidence of yeast infections after randomization	Whole	0.19	0.14	.05	IR=0.74
Sensitive, Competent Care of Child					
Beliefs associated with child abuse, Bavolek total score, 6-24 mo	Whole	100.5	98.7	.003	ES=-0.23
	Low-Resource	102.5	100.2	≤.01	ES=-0.29
Emotional/cognitive stimulation (Home total score) 12 & 24 mo	Whole	30.9	32.3	.003	ES=0.24
	Low-Resource	30.3	31.5	≤.05	ES=0.21
Child responsiveness, NCAST child total score, 6-24 mo	Whole	17.4	17.7	NS	ES=-0.09
	Low-Resource	17.2	17.9	≤.05	ES=-0.19
Injuries/Ingestions in Medical Record					
Incidence of encounters (all types)—Injuries/ingestions, 0-24 mo	Whole	0.56	0.43	.05	IR=0.77
	Low-Resource	0.67	0.41	≤.01	IR=0.61
Incidence of hospitalizations—Injuries/ingestions, 0-24 mo	Whole	0.03	0.01	.01	IR=0.33
	Low-Resource	0.04	0.01	<.10	IR=0.25
Incidence of days hospitalized—Injuries/ingestions, 0-24 mo	Whole	0.18	0.04	.0003	IR=0.22
	Low-Resource	0.26	0.02	≤.01	IR=0.08
Maternal Life-Course					
Count of Substances Used – child age 9	Whole	0.17	0.10	.075	IR=0.62

Count of closely spaced subsequent births – age 12	Whole	0.51	0.34	.019	IR=0.67
No. of Months with Partner, 6-12 years	Whole	57.89	68.11	.010	ES=-0.20
Food stamps use (avg. mos./yr), 0-12 years	Whole	7.19	6.54	.022	ES=0.13
AFDC/TANF use (avg. mos./yr), 0-12 years	Whole	5.30	4.69	.030	ES=0.12

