the first child's 18th birthday. The subsequent pregnancy variables were dropped as outcomes for this phase of the trial

Use of Welfare Services. We interviewed women to assess their use of TANF, food stamps, Medicaid, WIC, supplemental social security income, and subsidized child care, and abstracted Tennessee records of TANF, food stamps, and Medicaid use. Given that over 90% of the women live in Tennessee, Tennessee records provided reasonable estimates and were further supplemented by reported use of these services for periods the mother reported being outside of Tennessee. Delays in obtaining these administrative data delayed the final analysis of this report. Our primary outcomes are total government costs of women's use of SNAP, TANF/AFDC, and Medicaid over the 18-year period following birth of the first child.

Table 3. Outcome Domains and Sources of Data for Assessment of Maternal Life-Course and Health

Outcome Domain	In-person Interview	Admin Record	Biological Assay
Subsequent pregnancies	X		
Use of welfare services	X	X	
Substance Use and SUDs	X		
Relationship with partner	X		
Domestic Violence	X		
Maternal Depression	X		
Susceptibility Genes			X

Substance Use and SUDs. We obtained diagnoses of abuse and dependence on alcohol and 9 drugs or drug classes with the *Composite International Diagnostic Interview (CIDI)-Substance Abuse Module (CIDI-SAM)*, a structured, 30-to-60-minute interview designed for trained, lay interviewers. It is a descendent of the NIMH Diagnostic Interview Schedule. CIDI's reliability and validity^{186;187} made it the main assessment for DSM-IV Substance Field Trials and for the National Comorbidity Study.¹⁸⁸ Its validity has been documented in substance-dependent, conduct-disordered adolescents.¹⁸⁹ We used an ACASI version for making DSM-IV Abuse/Dependence diagnoses. We also assessed women's frequency of using substances with questions from the Drug Use Screening Inventory,¹⁹⁰ which assesses substance use based on measures of quantity and frequency of use of cigarettes, alcohol, and illegal substances. It also includes questions on severity of problems created in 10 domains of functioning.¹⁹⁰ Our primary outcome consisted of whether or not the mother abused or was dependent on any of the substances after she was randomized into her treatment condition.

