Inclusion of Gene Activity Classification Factors. Some of our models included classification factors for functional classifications (activity variants) of the polymorphisms hypothesized to moderate program impact in this trial (5-HTTLPR, MAOA-LPR, and COMT Val158Met); we were not interested in genotypes per se, but rather functional classes that group genotypes by activity level (low – L, high - H or intermediate - I). In the case of 5-HTTLPR, L_G and S alleles are both low-activity variants that lead to low expression; from the analysis standpoint, the low-activity genotypes (L_G/L_G, S/S, and L_G/S) were grouped into the low-activity class; the high activity genotypes (L_A/L_A) into a high-activity class; and the remaining genotypes (L_A/L_G and L_A/S) grouped into an intermediate class. We used a similar approach with MAOA-LPR and COMT Val158Met. In the case of the X-linked MAOA-LPR, we grouped males into high and low expression allele groups and excluded females from analyses. In the COMT Val158Met analyses, we excluded non-African ancestry participants.

Tests of Hypotheses

Maternal Outcome Hypotheses

Hypothesis 1 (primary): The program will continue to improve maternal life-course reflected in total costs for welfare (SNAP, AFDC/TANF, and Medicaid), especially for mothers with high psychological resources. We tested Hypothesis 1 by examining the primary maternal life-course outcome (public expenditures for SNAP, AFDC/TANF and Medicaid) in our primary model, estimating public expenditures for these benefits over time, which included a factor for T and P, the interaction between these classification factors (T x P), and a set of covariates. For the public benefit expenditure outcome, we analyzed the data in mixed models that included, in addition to the core model terms, women as levels of a random factor, a fixed repeated measures classification factor for time (first-born child age) of assessment, and all interactions of time with the other fixed classification factors. We examined the treatment–control difference summing across levels of maternal psychological resources, and conducted planned contrasts for women in the high-resource group.

Hypothesis 2 (secondary). The program will reduce maternal SUDs and depression. We examined SUDs and depression by examining planned contrasts within the classification structure specified for Hypothesis 1, using generalized linear models, logistic for depression and SUD.

Child Outcome Hypotheses

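### Primary Hypothesis 1 claims a continuing maternal benefit, but its outcome is an 18-year cost total with 12 years already examined, and no named contrast isolates the years after age 12

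*Protocol*

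**What the plan says.** Under Hypotheses for Primary Grant, revised maternal Hypothesis 1 (primary) reads "The program will continue to improve maternal life-course (reflected in total costs of welfare", the components being SNAP, TANF and Medicaid. The statement under Tests of Hypotheses matches it: "The program will continue to improve maternal life-course reflected in total costs for welfare". The Use of Welfare Services section defines the outcome as the total cost to government of mothers' "use of SNAP, TANF/AFDC, and Medicaid over the 18-year period following birth of the first child".

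On what was known beforehand, the protocol is open: "We specified hypotheses based upon the pattern of results found through child age 12". The whole-sample Maternal Life-Course rows of Table 1 include:

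- "Food stamps use (avg. mos./yr), 0-12 years": 7.19 (comparison) against 6.54 (nurse), p=.022.
- "AFDC/TANF use (avg. mos./yr), 0-12 years": 5.30 against 4.69, p=.030.

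The model for Hypothesis 1 is a mixed model with treatment, maternal psychological resources, their interaction, a repeated-measures factor for time (first-born child age), and the interactions of time with the other fixed factors. Two contrasts are named: the treatment difference taken across resource levels, and the treatment difference among high-resource mothers. Neither is tied to a period of the child's life.

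**The concern.** The word *continue* points to an effect in the new phase of follow-up. The Background section on early parental life course says as much, expecting the earlier life-course effects to last into the next phase. A total that starts at birth does not isolate that phase, because any saving from years 0-12 stays in it.

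If the 18-year total is significant, a reader may take it as evidence that benefit lasted beyond age 12, when the early difference alone could have produced it. This matters because the revision left welfare cost as the only primary maternal outcome. The policy question of whether savings persist would then rest on a test that cannot tell persistence from carry-forward.

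**Working it through.** The protocol gives no power, cost-share or correlation figure for this outcome, so there is no stated number to reproduce.

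**Share of years already examined.** 12/18 = 0.67. This is a share of years; no split of cost by child age is given.

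**What the known early difference leaves in the total if nothing follows.**
- Food stamps: 7.19 − 6.54 = 0.65 months/yr; 12 × 0.65 = 7.8 months; spread over 18 years, 7.8/18 = 0.43 months/yr.
- AFDC/TANF: 5.30 − 4.69 = 0.61 months/yr; 12 × 0.61 = 7.3 months; spread over 18 years, 0.41 months/yr.

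**Chance that the total is significant with no effect after age 12.** The inputs are:
- Early z-values from the Table 1 two-sided p-values: .022 gives zA = 2.29 and .030 gives zA = 2.17. Months of use stand in for cost (assumption).
- Weight w of years 0-12 in the total: assumed 2/3 by years, with range 0.5 to 0.8.
- Correlation r between early and later cost: assumed 0 to 0.9. Equal SDs of mean annual cost in the two periods are also assumed.

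With zB the later-period statistic, and s = √(w² + (1−w)² + 2rw(1−w)):

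z_total = (w·zA + (1−w)·zB) / s

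The early result is known, so zA is held fixed. If the early effect is real and equal to its estimate, and the later effect is zero, then zB ~ N(0, 1−r²), and

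P(z_total > 1.96) = 1 − Φ{ [(1.96·s − w·zA)/(1−w)] / √(1−r²) }

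Example with w = 2/3, r = 0.3, zA = 2.29: s = √(0.444 + 0.111 + 0.133) = 0.830. The expected z_total is 1.527/0.830 = 1.84. The threshold for zB is (1.627 − 1.527) × 3 = 0.30. Then 0.30/0.954 = 0.31, and P = 0.38.

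| w | zA | r = 0 | 0.3 | 0.5 | 0.7 | 0.9 |
|---|---|---|---|---|---|---|
| 0.5 | 2.29 | 0.315 | 0.181 | 0.101 | 0.032 | 0.000 |
| 0.5 | 2.17 | 0.274 | 0.150 | 0.079 | 0.022 | 0.000 |
| 2/3 | 2.29 | 0.578 | 0.377 | 0.242 | 0.106 | 0.004 |
| 2/3 | 2.17 | 0.483 | 0.286 | 0.164 | 0.056 | 0.001 |
| 0.8 | 2.29 | 0.860 | 0.710 | 0.582 | 0.413 | 0.135 |
| 0.8 | 2.17 | 0.725 | 0.520 | 0.364 | 0.186 | 0.014 |

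If the early difference was instead chance, zB ~ N(r·zA, 1−r²). At w = 2/3 the probability is then 0.48 to 0.84 for r from 0 to 0.7.

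**The case against.** The strongest reply is that the hypothesis defines its own measure as total welfare cost. Cumulative government cost is a coherent quantity and fits the benefit-cost aims. If the program truly lowered cost in years 0-12 and did nothing later, the 18-year total truly differs, and rejecting its null is correct. That stands. The probabilities above are error rates only for the claim of an effect after age 12. For the cumulative claim with a real early effect, they are not false-positive rates.

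The protocol is also open about basing its hypotheses on age-12 results. It adds that "These refined hypotheses were specified prior to the completion of data gathering and any analysis of treatment-control differences", which cannot cover the years already reported in Table 1. Its list of figures includes welfare expenditure by year for the whole, high-resource and low-resource samples (Figures 9-11), so a reader could see the later pattern. That helps, but a plot is not a named test.

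Three stronger readings are tempting, and the document does not support them:

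- **That two-thirds of the cost total was already known to favor the program.** Two-thirds is a share of years. Table 1 covers two of the three components, in months of use and for the whole sample only. An age-12 report in the reference list mentions government spending in its title, but its figures are not given.
- **That the stated contrast sums over time.** The Hypothesis 1 text sums over resource levels. The cumulative character comes from the outcome definition, and the model already carries treatment-by-time terms.
- **That the error rate is necessarily far above 5%.** Redrawing the early result at random around its estimate gives 0.28 to 0.53 for SE ratios (later to early period) and correlations of 0.3 to 0.7. That treats a known result as unknown, and it still rests on inputs the protocol does not give.

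A statistical analysis plan might add a period contrast. The point here is narrower: the protocol itself pairs a hypothesis of continuation with named contrasts that do not address it.

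**Conclusion.** The mismatch between the hypothesis and its named test is clear from the text; its size is uncertain. With two-thirds weight on years 0-12, a real early effect and correlation 0 to 0.7, a significant total favoring the program with no later effect has conditional probability of about 0.06 to 0.58, against 0.025 nominal. It is higher at weight 0.8. It is near zero at correlation 0.9 for weights up to two-thirds. At half weight it is 0.02 to 0.32 for correlations up to 0.7.

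These figures use months of food stamps and AFDC/TANF in place of cost, and they say nothing about Medicaid or the high-resource contrast. The supported conclusion is that a significant 18-year total would not by itself show that benefit continued. The cumulative analysis itself remains valid.

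**What to change.** Keep the 0-18-year total as the cumulative cost estimate, and describe its test as a test of a cumulative effect. From the mixed model already planned, name a treatment contrast for the years after age 12, for all mothers and for high-resource mothers, as the test of continuation. Report the 0-12 and later-period estimates side by side with confidence intervals.

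The cost is one additional contrast in each of the two groups, from a model that already holds the required terms, with no new data. The later-period contrast has less power than the total, so a non-significant result should not be read as proof that benefit stopped. Nor does it fully remove dependence on the early data. If the early difference was chance and r = 0.5 with zA = 2.29, it reaches significance with conditional probability 1 − Φ((1.96 − 1.145)/0.866) = 0.17, compared with 0.73 for the total at two-thirds weight.

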Sexual Behaviors. We assessed reports of specific sexual behaviors for adolescents in the ACASI section of the interview. We assessed age of first sexual experience (oral, vaginal, and anal sex), number of lifetime male and female partners, and the number of partners in the last three months. Retrospective recall of sexual behaviors is stable for intervals as long as 3 months.^{211;212} Given that many adolescents engage in sexual behavior on infrequent or episodic bases,²¹³ we chose an assessment interval of 3 months to maximize our ability to detect sexual behavior without compromising reliability. Information will be elicited over the past 3 months on: number of different sexual partners, detailed questions on the incidence of protected and unprotected oral, vaginal, and anal sex. Additional questions addressed the number of treated sexually transmitted infections (STI) over the lifetime, whether the respondent ever had sex for money, drugs, or food. Participants estimated the number of occasions in which they engaged in protected and unprotected vaginal and anal intercourse using a format developed by St. Lawrence.²¹⁴

Risk for HIV Infection. We created an HIV risk score taking into account the following factors: gender, type of intercourse (vaginal, anal), number of partners, and the probability of sexual transmission of HIV within the Memphis/Shelby County community. The HIV risk transmission index score was created using a modified Bernoulli process model (Pinkerton and Abramson, 1998).²¹⁵ The probability of HIV acquisition was calculated as follows:

Probability of HIV acquisition =

$$\pi [1-(1-\alpha \text{UVI})^n (1-\alpha \text{PVI})^n (1-\alpha \text{UAI})^n (1-\alpha \text{PAI})^n]$$

- “ π ” represents the prevalence of HIV within a population. Prevalence of HIV in Shelby County in 2012 was estimated at a rate of 655.6 for African American and 139.3 for Caucasian per 100,000 (Shelby County Health Department, 2012). Mother's race at intake was used for child's race.
- “ n ” represents the number of acts performed over a three month period
- “ α ” represents the probability of HIV transmission per sexual act. Sexual acts are

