Hypothesis 3a–d (primary): The program will improve the health and development of firstborn children who will exhibit: a) superior cognitive, language, and academic functioning; b) less depression and anxiety; c) less gang membership, and fewer arrests, convictions, and self-reported antisocial behavior - especially for crimes involving interpersonal violence.. We will examine this hypothesis in the model used to test hypotheses 1 and 2, after adding child sex (S) as a classification factor. We will test hypotheses 3a–d by examining each of child outcome in the saturated TxPxS (2x2x2) model, including covariates. In our first-level analysis, we will examine treatment–control differences averaging across levels of maternal psychological resources and child sex. Outcomes that have essentially normal distributions (e.g., cognitive and academic outcomes) will be examined in the general linear model. Those that have low-frequency count distributions (e.g., counts of failed conduct grades) will be examined in the generalized model. For very sparsely distributed outcomes, we may need to drop certain model terms, such as 3-way interactions or nonsignificant covariates to increase model stability. We will retain model terms with highest levels of significance and those central to the hypothesis. Finally, we will examine outcomes that have binomial distributions in the fully specified logistic model. Some outcomes, such as standardized math scores, will have multiple measures for each child at different ages, and the model will include additional repeated measures factors for child age.

Hypothesis 4 a–c (primary): The program will reduce youth risk for a) HIV infection, b) pregnancies, births, c) use of substances, and SUDs. We will employ nearly identical analytic methods for testing hypothesis 4 as we employ for testing hypothesis 3. The primary outcome(s) for HIV risk will consist of indices that we will create to quantify HIV risk exposure.

Hypothesis 5 (secondary): The program will improve firstborn children’s executive cognitive functioning (ECF); and rates of high school graduation. We will employ nearly identical analytic methods

for testing hypothesis 5 as we employ for testing hypothesis 3.. In analysis of executive cognitive functions, we will control statistically for KBIT matrices scores and PPVT to discern the impact of the program on executive functions independent of general intelligence and language.

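### The HIV risk score is said to use number of partners, but its printed formula has no partner term, so at a fixed number of acts it gives the same score for any number of partners

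*Protocol*

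**What the plan says.** In the Protocol, under Child Assessments, Risk for HIV Infection, the score is introduced with its inputs: "We created an HIV risk score taking into account the following factors: gender, type of intercourse (vaginal, anal), number of partners", followed by the probability of sexual transmission in the local community. The method is described as follows: "The HIV risk transmission index score was created using a modified Bernoulli process model". The modification is not described.

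The printed probability of acquisition is π multiplied by one minus the product of four terms (1 − α)^n. There is one term for each act type: unprotected and protected vaginal, unprotected and protected anal. The symbols are defined as:

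- π is population prevalence, "estimated at a rate of 655.6 for African American and 139.3 for Caucasian per 100,000", with the mother's race at intake standing in for the child's.
- n "represents the number of acts performed over a three month period".
- α "represents the probability of HIV transmission per sexual act". Its values are attributed to an outside source and are not printed.

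The partner's gender is used, with the participant's, to label acts as insertive or receptive. The number of partners does not enter.

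The Sexual Behaviors paragraph shows that partner number was collected for the same window: "Information will be elicited over the past 3 months on: number of different sexual partners".

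Under Tests of Hypotheses, Hypothesis 4 (primary) states: "The primary outcome(s) for HIV risk will consist of indices that we will create to quantify HIV risk exposure". The score above is the only such index that the protocol describes.

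**The concern.** The list of inputs and the formula cannot both be right. Either the score was calculated as printed and the description is wrong, or a partner-adjusted score was calculated and the formula is wrong. A reader cannot tell which.

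The difference affects what the index measures. Multiplying once by π treats the youth as meeting a single draw from the infected-or-not distribution, however many partners there were. If partners are infected independently, each new partner is a new draw. For the same number of acts, spreading them over more partners then raises the risk. The printed score does not respond to that, although partner number is offered as one of its components and the index serves a primary hypothesis.

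**Working it through.** **Inputs from the protocol.** π = 655.6/100,000 = 0.006556 (African American) or 139.3/100,000 = 0.001393 (Caucasian). The quantity n is acts in three months. The number of partners m over the same three months was collected. No value of α is printed and no numeric score is given, so there is no figure of the protocol's to reproduce.

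**Assumed inputs.** α from 0.0005 to 0.014, one act type at a time, with illustrative pairs (n, m).

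**Formulas.** For one act type:

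- Printed: P = π[1 − (1 − α)^n]
- Partner-level, independent partners, acts split evenly: P = 1 − {1 − π[1 − (1 − α)^(n/m)]}^m

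At m = 1 the second reduces to the first, so the printed formula is the one-partner case.

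**Ceiling.** As n grows, the printed score tends to π whatever m is. The partner-level score tends to 1 − (1 − π)^m.

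| m | Printed, π = 0.006556 | Partner-level, π = 0.006556 | Printed, π = 0.001393 | Partner-level, π = 0.001393 |
|---|---|---|---|---|
| 1 | 0.00656 | 0.00656 | 0.00139 | 0.00139 |
| 2 | 0.00656 | 0.01307 | 0.00139 | 0.00278 |
| 5 | 0.00656 | 0.03235 | 0.00139 | 0.00695 |
| 10 | 0.00656 | 0.06366 | 0.00139 | 0.01384 |

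**Worked case.** Take α = 0.014, n = 100, m = 10, π = 0.006556.

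- Printed: 0.986^100 = 0.2442, so P = 0.006556 × 0.7558 = 0.00496, or 496 per 100,000.
- Partner-level: 0.986^10 = 0.8685. The risk per partner is 0.006556 × 0.1315 = 0.000862, so P = 1 − (1 − 0.000862)^10 = 0.00859, or 859 per 100,000.
- Ratio: 1.73.

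**Ratio of partner-level to printed score, π = 0.006556.**

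| α | 12 acts, 4 partners | 30 acts, 5 partners | 60 acts, 6 partners | 100 acts, 10 partners |
|---|---|---|---|---|
| 0.0005 | 1.002 | 1.006 | 1.01 | 1.02 |
| 0.001 | 1.004 | 1.01 | 1.02 | 1.05 |
| 0.005 | 1.02 | 1.06 | 1.13 | 1.24 |
| 0.014 | 1.06 | 1.17 | 1.38 | 1.73 |

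The ratios at π = 0.001393 are almost the same. An assumed α above this range widens the gap: at α = 0.05 with 90 acts and 5 partners the ratio is 3.02.

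**Mixed acts.** With 90 acts at α = 0.001 and 10 at α = 0.014, ten partners and π = 0.006556, the printed score is 135 per 100,000 and the partner-level score 150, a ratio of 1.11.

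**When acts change too.** At α = 0.001 and π = 0.006556 the printed score is 32.0 per 100,000 for 50 acts and 6.5 for 10 acts. The partner-level score for 50 acts over five partners is 32.6. A fall in partners that brings a fall in acts is therefore registered by the printed score almost as well as by the partner-level one.

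**The case against.** The strongest reply is that the gap hardly matters in practice. When α is small, risk is close to linear in acts under either formula, so low sensitivity to partner number comes from the Bernoulli model itself more than from the omission. The largest ratio in the table needs 100 acts, all at α = 0.014, with ten partners in three months. The protocol itself notes that many adolescents have sex infrequently or episodically. The ceiling is also remote at low infectivity: at α = 0.001 the printed score reaches 3% of π at 30 acts and 9.5% at 100. All of this stands, and it limits the size of the point.

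It is also fair to say that the single multiplication by π is valid if partners share one infection status, that the protocol calls its model modified, and that the replacement brings assumptions of its own. But the modification is never described, and none of this puts a partner count into the printed formula.

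A reader might go further in three ways that the document does not support:

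- **Any benefit through fewer partners is invisible.** It is not: the score falls when fewer partners means fewer acts. Only a change in partners at fixed acts is missed.
- **The arm difference is shrunk toward zero.** The ratios above are for individual scores. No arm comparison has been computed, and the effect on it depends on how acts, act types and partners differ between arms.
- **The background section shows that multiple partners in the scoring window are common and central to the HIV rationale.** The figure there, 31% with four or more partners by 11th grade, is cumulative and says nothing about a three-month window. That section gives at least as much weight to substance use and sexually transmitted infections.

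Nor is this score necessarily the only primary measure of HIV risk: Hypothesis 4 allows for more than one index.

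**Conclusion.** The point holds as a contradiction between the stated inputs and the printed formula of an index that serves a primary hypothesis. As printed, the score does not depend on partner number at fixed acts, equals the single-partner (or shared-status) case, and is capped at 0.656% or 0.139%.

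The numerical understatement is small for low-infectivity acts, about 1 to 5% at α = 0.001 for 30 acts with 5 partners up to 100 acts with 10. It is material only for many higher-infectivity acts with several partners, up to about 1.7 times at α = 0.014 with 100 acts and 10 partners. These sizes rest on assumed α and act counts, independent partners and an even split of acts. The contradiction, the insensitivity and the cap do not rest on the assumed values. The point should be corrected, but it does not by itself undermine Hypothesis 4.

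**What to change.** First establish which formula was used. Then choose one of two courses.

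1. **Preferred: make the index match its description.** Compute it as 1 − {1 − π[1 − Π_k(1 − α_k)^(n_k/m)]}^m, where k runs over the act types, n_k is the count for each type, and m is the 3-month partner count already collected. Set the score to 0 when m = 0, after checking any record that reports acts but no partner. State the assumptions that partners are independent and that acts are spread evenly over them. Report the 3-month number of partners by arm beside the index.
2. **If the printed formula is kept,** remove partner number from the listed inputs and state that the index does not reflect it.

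The protocol's list of tables includes HIV risk estimates at age 18 (Table 14), so the index may already have been analyzed. In that case, show the results under both formulas, so that the change does not look like a choice made after seeing the data.

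The cost is the recalculation of one derived variable, with no new data. The drawback of the first course is the even-split assumption, which the collected counts may not allow to be checked.
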